8.3 Sample Size and Power Calculations

Sample size calculation is based on data from GO-RAISE registrational study in which golimumab was evaluated in patients with AS [18-21]. The baseline BASFI was 5.0 which changed by mean (\pm SD, standard deviation) $-2.5 (\pm 2.12)$ at week 52 (approximately 12 months) [19].

Sample size formula evaluation is $n = f(\alpha, \beta/2) \times 2 \times \sigma^2/d^2$ where:

n is sample size;

α is type 1 error = 5%;

β is type 2 error = 10%;

σ is standard deviation;

d is equivalents limit;

$f(\alpha, \beta) = [\Phi-1(\alpha) + \Phi-1(\beta)]^2$ where Φ is cumulative distribution function for the normal distribution.

Product: MK-8259
Protocol/Amendment No.: 021
VEAP ID NO: 6189
Date: 15-January-2018

Power of the study is 90% with formula evaluation $P = 1-\beta$ where:

P is power;

β is type 2 error = 10%.

Thus, the analysis of the data shows that the minimum necessary sample size should be at least 18 patients to show a statistically significant change of BASFI from baseline to 12 months.

On this basis and considering that the dropout rate over the two years of the study is expected to be about 30% (ranging from 21% in a randomized controlled study [19] to 37% in real clinical practice [25]), it is decided that the necessary number of patients to be included into the study should be 39 individuals. It is expected that at least 27 patients will be included in the patient set completing the study.

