Statistical Methods	Quantitative variables will be tested for normal distribution using the Shapiro-Wilk test. The hypothesis of equality of variances will be tested using Levene's test. Quantitative variables matching a normal distribution will be described in terms of the mean \pm standard deviation, and values outside of the normal distribution as medians, 25% and 75% quartiles. Qualitative variables will be presented in the form of percentages of the absolute value N.
Sample Size and Power Calculations	Sample size calculation is based on data from GO-RAISE registration study in which golimumab was evaluated in patients with AS. The baseline BASFI was 5.0 which changed by mean (\pm SD, standard deviation) $-2.5 (\pm 2.12)$ at week 52 (approximately 12 months). The analysis of the data shows that the minimum necessary sample size should be 18 patients to show a statistically significant change of BASFI from baseline to 12 months. On this basis and considering that the dropout rate over the two years is expected to be 30%, we decided that the necessary number of patients to be included into protocol should be 39 individuals. It is expected that around 27 patients will be included in the patient set completing the study. Power of the study is 90% with formula evaluation $P = 1-\beta$ where P is power and β is type 2 error = 10%.
Limitations	In this non-interventional study the quality of the data is important. Therefore, it is important for the sponsor or designee to monitor data completion and perform quality checks during the course of the study. To minimize missing data, a set of core variables is required to be available at enrollment as part of inclusion criteria.

Product: MK-8259

Protocol/Amendment No.: 021

VEAP ID NO: 6189

Date: 15-January-2018

1 Background and Rationale

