3 METHODOLOGY

3.1 Summary of Study Design

This study is a non-interventional prospective observational cohort study. Patients participating after signing informed consent form will receive treatment and diagnostic procedures according to daily clinical practice conducted by his/her physician.

Visits during the study will include collection of data if already available. There are no procedures that are required as part of this study.

The study is to be conducted in multiple centers across Russia. AS patients with coxitis newly prescribed golimumab during the course of usual clinical care, will be enrolled and followed prospectively for 24 months with data collection at the approximate time points: baseline (pre-treatment) and consequent every 6 months. A time window of approximately \pm 6 weeks is envisaged for follow-up visits.

Product: MK-8259

Protocol/Amendment No.: 021

VEAP ID NO: 6189

Date: 15-January-2018

Patients will be screened and selected according to inclusion and exclusion criteria prior to enrollment. The study centers will maintain a list of all screened patients with the reasons for excluding patients being enrolled into the study.

Baseline data will be extracted from medical records (MR), if available at each treatment center. No additional interventional tests or medical procedures such as additional blood samples, X-ray or other technical investigations will be performed as a part of this study. If any data element is not available it will be reported as missing.

At baseline, data on age, gender, occupational status, AS and coxitis symptoms duration, concomitant disease, will be collected according to usual clinical practice.

C-reactive protein (CRP) is usually measured as part of the normal screening for patients prior to the initiation of a biologic agent in clinical practice. The results of this measurements will be collected. No additional blood withdrawals will be necessary for the study. CRP will be collected at baseline and at 6, 12, 18, 24 months if the measurements are available in regular clinical practice. Human leukocyte antigen B27 (HLA-B27) status (i.e. positive or negative) will be collected at baseline if available. Most AS patients will have this test performed as part of the diagnostic work-up in clinical practice.

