8.2.2 Limitations

In this non-interventional study the quality of the data is important. Therefore, it is important for the sponsor or designee to monitor data completion and perform quality checks during the course of the study. To minimize missing data, a set of core variables is required to be available at enrollment as part of inclusion criteria.

This study will collect data on patients being treated in real clinical Rheumatology practice. It is expected that the number of patients dropping out before completion of the whole course of observation will be about 30%. To minimize this limitation, the study will enroll 39 patients to ensure that the number of subjects entering the analysis *Per Protocol* will be enough (27 subjects). In addition, secondary analyses will evaluate data on completers vs patients dropping out before completion separately.

The potential issue of missing data is limitation of the study. To minimize this limitation, patients with missing data are planned to enter the analysis of LOCF. Data recorded on the last visits of patients or the visit after the missing one will contribute to the analysis.

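### Section 8.3 sizes a single-cohort paired comparison with an equivalence-type formula: 18 patients at 90% power does not describe the planned test, and 39 does not follow from 18 (conservative on the stated inputs; minor)

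*Combined protocol and SAP*

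**What the plan says.** Section 3.1 describes one cohort: "This study is a non-interventional prospective observational cohort study". Section 8.1.2 makes the BASFI change from baseline to 12 months the primary measure. Section 8.1 plans a paired t-test, with the Wilcoxon signed rank test if the normality or variance criteria fail.

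Section 8.3 takes its inputs from the GO-RAISE study: a BASFI change of -2.5 with SD 2.12 at week 52. It prints n = f(α, β/2) × 2 × σ²/d², with α = 5% and β = 10%, and explains the last symbol only as "d is equivalents limit". It then says "Power of the study is 90% with formula evaluation" P = 1-β, and gives this conclusion: "minimum necessary sample size should be at least 18 patients to show a statistically significant change of BASFI from baseline to 12 months".

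Taking this together with two-year dropout of about 30% (range 21% to 37%), the section sets enrolment at 39 and adds: "It is expected that at least 27 patients will be included in the patient set completing the study". The Protocol Summary repeats 18, 39 and 90%, but is softer on completers: "It is expected that around 27 patients will be included in the patient set completing the study". Section 8.2.2 calls 27 patients in the Per Protocol analysis sufficient and gives no calculation.

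**The concern.** A sample size section should let a reader get from the stated inputs to the stated number using the test that will be run. Here the factor 2, the halved β and the equivalence limit fit an equivalence comparison, usually one of two groups. The section's own conclusion is about showing a significant change within one group, and d has no value.

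Three things are affected: whether 18 can be reproduced, whether 90% is the power of the planned test at that size, and whether 39 follows from 18. The figure 18 is also the trigger for the interim analysis (Sections 6.1.2.3 and 8.1.1). If the error ran the other way, the primary objective would be at risk, so its direction has to be checked.

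**Working it through.** **Inputs.** From Section 8.3: change 2.5, SD 2.12 (attached there to the change), α = 5%, β = 10%, dropout 30% (21% to 37%) over two years. From Section 8.1: paired t-test or Wilcoxon signed rank. Assumptions: d = 2.5, because no value is given; two-sided testing, because sidedness is not stated for the primary test.

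**1. The plan's own figure.** f(0.05, 0.05) = (1.645 + 1.645)² = 10.82. Then n = 10.82 × 2 × 2.12²/2.5² = 15.56, i.e. 16. Other choices of the error terms:

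| Error terms | f | n with factor 2 | n without it |
|---|---|---|---|
| α, β/2 (as printed) | 10.82 | 15.56 → 16 | 7.78 → 8 |
| α, β | 8.56 | 12.32 → 13 | 6.16 → 7 |
| α/2, β | 10.51 | 15.11 → 16 | 7.56 → 8 |
| α/2, β/2 | 12.99 | 18.69 → 19 | 9.34 → 10 |

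None rounds up to 18. The printed formula does so only for d between about 2.32 and 2.39 (15.56 × 2.5² = 97.28; √(97.28/18) = 2.325; √(97.28/17) = 2.392). No such value is stated.

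**2. The planned test on the stated inputs.** The paired formula is n = (z₁₋α/₂ + z₁₋β)² × SD²/δ² = 10.51 × 2.12²/2.5² = 7.56, i.e. 8 before the t correction. Exact power from the noncentral t distribution, with noncentrality 2.5√n/2.12:

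| n | Power |
|---|---|
| 9 | 87.1% |
| 10 | 91.1% |
| 18 | 99.7% |
| 27 | over 99.9% |

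So 10 patients suffice for 90%. The Wilcoxon fallback, simulated with normal data, gives about 90% at n = 10, 92% at n = 11 and over 99% at n = 18. The choice of test does not change the picture.

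**3. Can a paired test yield 18?** Yes, if 2.12 is read as a single-visit SD with zero correlation between visits. The SD of change is then 2.12 × √2 = 3.00, and power is 89.7% at n = 17, 91.5% at n = 18 and 99% at n = 27. At a correlation of 0.3 the SD of change is 2.51 and n = 13; at 0.7 it is 1.64 and n = 7.

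**4. From 18 to 39.** 18/0.70 = 25.7, i.e. 26 (23 at 21% dropout, 29 at 37%). 27/0.70 = 38.6, i.e. 39. So 39 follows from 27, and nothing derives 27 from 18.

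**5. Completers from 39.** 39 × 0.79 = 30.8; 39 × 0.70 = 27.3; 39 × 0.63 = 24.6. A floor of 27 fails at the plan's own upper dropout rate.

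**6. Margin for the primary test.** At n = 18 the paired t-test keeps 90% power for a change of 2.5 up to an SD of change of 3.08, or with SD 2.12 down to a change of 1.72. At n = 27 the 95% confidence interval half-width is 2.056 × 2.12/√27 = 0.84, or 1.19 with SD 3.00.

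**The case against.** The strongest reply is that 2σ² need not mean two groups. It is also the variance of the difference between two uncorrelated measurements on the same patient, and under that reading 18 is the smallest n at which the planned paired t-test reaches 90% (step 3). This stands in part: a two-group calculation is not the only possible source of 18, and a mislabelled SD is possible. It does not rescue the text. Section 8.3 attaches 2.12 to the change, and the reading leaves β/2, the equivalence limit and the step to 39 unexplained.

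Second, 90% is entered as a design input (1-β), and the section never says in so many words that power at 18 equals 90%. That is fair, and on the stated inputs 90% is exceeded. But a minimum of 18 at 90% power invites exactly that reading, and for the planned test the minimum is about 10.

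Third, 27 is a two-year completer count. The primary measure is at 12 months, and Sections 2.3, 8.2.1 and 8.2.2 bring dropouts in through LOCF. This stands: figures at n = 27 describe a completer (Per Protocol) scenario, not the expected n of the primary analysis.

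Fourth, the lower bound of 27 is only an expectation at about 30% dropout, and the Protocol Summary already says around 27. That makes it a small point, though the two passages should agree.

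**Conclusion.** The stated size and power do not describe the planned test, and the section's chain from 18 to 39 does not hold. On the stated inputs the planned test needs about 10 patients for 90% power and has 99.7% at 18. With 30% dropout, 18 leads to 26 enrolled, not 39. This rests on two-sided 5% and on 2.12 being the SD of the change, as printed. If the SD of change were 3.00, power at 18 would be 91.5%, still above 90%.

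A reader might infer that the primary test is underpowered. The documents do not support that: the error is conservative under either reading of the SD. A reader might also infer that 39 is too many and that enrolment could be cut. That does not follow either, because Section 1.1 says the source study did not include patients with coxitis, so change and SD may not carry over. Nor do the documents show that 27 is wrong; they only fail to say where it comes from.

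Severity is minor: a defect of documentation and justification.

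**What to change.** Wording only, in Sections 8.3 and 8.2.2 and the Protocol Summary:

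1. Replace the formula with the paired one, n = (z₁₋α/₂ + z₁₋β)² × SD²/δ² with t correction. State δ, two-sided α, and whether 2.12 is the SD of the change or of a single visit.
2. Restate the power for the planned test: 99.7% at n = 18 and over 99.9% at n = 27 if 2.12 is the SD of change; 91.5% and 99% if the SD of change is 3.00. Mark these as conditional on inputs from a study without coxitis patients. Label n = 27 as the two-year completer (Per Protocol) scenario, since the primary endpoint is at 12 months and LOCF brings dropouts in.
3. Keep 39 and have the sponsor state its actual basis for 27, rather than a rationale supplied afterwards. Expected precision can be added: 95% half-width 0.84 at n = 27 with SD 2.12, 1.19 with SD 3.00.
4. Replace the lower bound of 27 completers with about 27 (about 25 to 31 over 37% to 21% dropout), in line with the Protocol Summary.

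Cost: a text amendment. Enrolment, visits, data and the interim trigger do not change.

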9.2 Compliance with Financial Disclosure Requirements

Financial Disclosure requirements are outlined in the US Food and Drug Administration Regulations, Financial Disclosure by Clinical Investigators (21 CFR Part 54). It is the Sponsor's responsibility to determine, based on these regulations, whether a request for Financial Disclosure information is required. It is the investigator's/subinvestigator's responsibility to comply with any such request.

The investigator/subinvestigator(s) agree, if requested by the Sponsor in accordance with 21 CFR Part 54, to provide his/her financial interests in and/or arrangements with the Sponsor to allow for the submission of complete and accurate certification and disclosure statements. The investigator/subinvestigator(s) further agree to provide this information on a Certification/Disclosure Form, commonly known as a financial disclosure form, provided by the Sponsor or through a secure password-protected electronic portal provided by the Sponsor. The investigator/subinvestigator(s) also consent to the transmission of this information to the Sponsor in the United States for these purposes. This may involve the transmission of information to countries that do not have laws protecting personal data.

9.3 Compliance with Law, Audit and Debarment

By signing this protocol, the investigator agrees to conduct the study in an efficient and diligent manner and in conformance with this protocol; generally accepted standards of Good Pharmacoepidemiology Practice; and all applicable local laws, rules and regulations relating to the conduct of the clinical study.

The investigator also agrees to allow monitoring, audits, Institutional Review Board/Independent Ethics Committee review and regulatory agency inspection of study-related documents and procedures and provide for direct access to all study-related source data and documents.

The investigator agrees not to seek reimbursement from subjects, their insurance providers or from government programs for procedures included as part of the study reimbursed to the investigator by the Sponsor.

The Investigator shall prepare and maintain complete and accurate study documentation in compliance with Good Pharmacoepidemiology Practice, standards and applicable local laws, rules and regulations;

Product: MK-8259

Protocol/Amendment No.: 021

VEAP ID NO: 6189

Date: 15-January-2018

and, for each subject participating in the study, provide all data, and, upon completion or termination of the study, submit any other reports to the Sponsor as required by this protocol or as otherwise required pursuant to any agreement with the Sponsor.

Study documentation will be promptly and fully disclosed to the Sponsor by the investigator upon request and also shall be made available at the investigator's site upon request for inspection, copying, review and audit at reasonable times by representatives of the Sponsor or any regulatory agencies. The investigator agrees to promptly take any reasonable steps that are requested by the Sponsor as a result of an audit to cure deficiencies in the study documentation and worksheets/case report forms.

The investigator must maintain copies of all documentation and records relating to the conduct of the study in accordance with their institution's records retention schedule which is compliant with all applicable regional and national laws and regulatory requirements. If an institution does not have a records retention schedule to manage its records long-term, the investigator must maintain all documentation and records relating to the conduct of the study for 5 years after final report or first publication of study results, whichever comes later, per GPP guidelines. This documentation includes, but is not limited to, the protocol, worksheets/case report forms, advertising for subject participation, adverse event reports, subject source data, correspondence with regulatory authorities and IRBs/ERCs, consent forms, investigator's curricula vitae, monitor visit logs, laboratory reference ranges, laboratory certification or quality control procedures and laboratory director curriculum vitae. All study documents shall be made available if required by relevant regulatory authorities. The investigator must consult with the Sponsor prior to discarding study and/or subject files.

The investigator will promptly inform the Sponsor of any regulatory agency inspection conducted for this study.

Persons debarred from conducting or working on studies by any court or regulatory agency will not be allowed to conduct or work on this Sponsor's studies. The investigator will immediately disclose in writing to the Sponsor if any person who is involved in conducting the study is debarred or if any proceeding for debarment is pending or, to the best of the investigator's knowledge, threatened.

In the event the Sponsor prematurely terminates a particular study site, the Sponsor will promptly notify that site's IRB/IEC.

According to European legislation, a Sponsor must designate an overall coordinating investigator for a multi-center study (including multinational). When more than one study site is open in an EU country, Merck, as the Sponsor, will designate, per country, a national principal coordinator (Protocol CI), responsible for coordinating the work of the principal investigators at the different sites in that Member State, according to national regulations. For a single-center study, the Protocol CI is the principal investigator. In addition, the Sponsor must designate a principal or coordinating investigator to review the study report that summarizes the study results and confirm that, to the best of his/her knowledge, the report accurately describes the conduct and results of the study in the study's final report. The Sponsor may consider one or more factors in the selection of the individual to serve as the Protocol CI and/or CSR CI (e.g., availability of the CI during the anticipated review process, thorough understanding of study methods, appropriate enrollment of subject cohort, timely achievement of study milestones). The Protocol CI must be a participating study investigator.

Product: MK-8259

Protocol/Amendment No.: 021

VEAP ID NO: 6189

Date: 15-January-2018

9.4 Compliance with Study Registration and Results Posting Requirements

Under the terms of the Food and Drug Administration Modernization Act (FDAMA) and the Food and Drug Administration Amendments Act (FDAAA), the Sponsor of the study is solely responsible for determining whether the study and its results are subject to the requirements for submission to the Clinical Trials Data Bank, www.clinicaltrials.gov. Merck, as Sponsor of this study, will review this protocol and submit the information necessary to fulfill these requirements. Merck entries are not limited to FDAMA/FDAAA mandated studies. Information posted will allow subjects to identify potentially appropriate studies for their disease conditions and pursue participation by calling a central contact number for further information on appropriate study locations and site contact information.

By signing this protocol, the investigator acknowledges that the statutory obligations under FDAMA/FDAAA are that of the Sponsor and agrees not to submit any information about this study or its results to the Clinical Trials Data Bank.

9.5 Quality Management System

By signing this protocol, the Sponsor agrees to be responsible for implementing and maintaining a quality management system with written development procedures and functional area standard operating procedures (SOPs) to ensure that studies are conducted and data are generated, documented, and reported in compliance with the protocol, accepted standards of Good Pharmacoepidemiology Practice, and all applicable federal, state, and local laws, rules and regulations relating to the conduct of the study.

9.6 Data Management

The investigator or qualified designee is responsible for recording and verifying the accuracy of subject data. By signing this protocol, the investigator acknowledges that his/her electronic signature is the legally binding equivalent of a written signature. By entering his/her electronic signature, the investigator confirms that all recorded data have been verified as accurate.

For an outsourced study the institutional policies of the vendor should be followed for development of data management plans. However, the vendor should ensure compliance with Good Pharmacoepidemiology Practice, and all applicable federal, state, and local laws, rules and regulations relating to the conduct of the study

10 List of abbreviations

AE	Adverse event
AR	Adverse reaction
AS	Ankylosing Spondylitis
ASDAS	Ankylosing Spondylitis Disease Activity Score
BASDAI	Bath Ankylosing Spondylitis Activity Index
BASFI	Bath Ankylosing Spondylitis Functionality Index
BASMI	Bath Ankylosing Metrological Index
BASRI	Bath Ankylosing Radiology Index
CRF	Clinical Registration Form
CRP	C-reactive protein

Product: MK-8259
 Protocol/Amendment No.: 021
 VEAP ID NO: 6189
 Date: 15-January-2018

CSR	Clinical Study Report
DMARD	Disease Modifying Anti-Rheumatic Drugs
DSUR	Development Safety Update Report
ERC	Ethic Review Committee
FDAAA	Food and Drug Administration Amendments Act
FDAMA	Food and Drug Administration Modernization Act
HLA B27	Human Leukocyte Antigen B27
HOI	Health Outcomes of Interest
ICF	Informed Consent Form
IEC	Independent Ethics Committee
IRB	Independent Review Board
LOCF	Last Observation Carried Forward
MAH	Market Authorization Holder
MRI	Magnetic Resonance Imaging
NIS	Non-Interventional Study
NSAR	Non-Serious Adverse Reaction
Protocol CI	National Principal Coordinator
PSUR	Periodic Safety Update Report
SAE	Serious Adverse Event
STIR	Short Tau Inversion Recovery
TNF	Tumor Necrosis Factor
US	Ultrasound

11 List of References

